# PV will be detected manually.

Source: BI reference document 'Protocol Violation Handling Definitions' [001-MCS-50-413\_RD-01] (2).

Table 6.2: 1 Important protocol violations (continued)

Category / Code	Description	Comments	Excluded from
D2.01b	Use of prohibited med. on or after V2 or during the on-trt period, unless rescue trt. to stabilize a worsening disease cond. - prior to or on D14, without potential infl. on eff. data	See the list of restricted medication in CTP, Table 4.2.2.1: 1, manual assessment of potential influence at RPM/DBLM	None #
D2.02	Use of prohibited medication during treatment period when not provided as a rescue treatment to stabilize a worsening disease condition – after Day 14	See the list of restricted medication in CTP, Table 4.2.2.1: 1	None #
D3	Mandatory medication not taken		
D3.01	Any dose change in background medication on or after Visit 2 – prior to or on Day 14	Dose escalation of background therapy (methotrexate or retinoids) is not allowed within 4 weeks before Visit 2 (dose decrease is permitted). From Visit 2 to Visit 14 no change in dose of retinoids or methotrexate is allowed.	PPS, PKS, BMS, DSS, RSS
D3.02	Any dose change in background medication – after Day 14	Dose escalation of background therapy (methotrexate or retinoids) is not allowed within 4 weeks before Visit 2 (dose decrease is permitted). From Visit 2 to Visit 14 no change in dose of retinoids or methotrexate is allowed.	None
E	Missing data		
	None	Missing visits, evaluations, and tests will be considered missing data, not protocol violations	
F	Study specific analysis		
F1	Other trial specific violation		
F1.01	Study drug intake outside time window	Infusion period takes longer than 240 minutes.	None

# PV will be detected manually.

Violations F2.01 and F2.02 can only be detected at the trial site.

Source: BI reference document 'Protocol Violation Handling Definitions' [001-MCS-50-413\_RD-01] (2).

Table 6.2: 1 Important protocol violations (continued)

Category / Code	Description	Comments	Excluded from
F2	Certain violations of procedures used to measure secondary efficacy data		
F2.01	Evaluation of GPPASI or GPPGA for a given patient not performed by the same physician up to Week 2	GPPASI, GPPGA assessments up to Week 2 for a given patient are not performed by the same physician.	PPS #
F2.02	Evaluation of GPPASI or GPPGA for a given patient not performed by the same physician throughout the study	GPPASI, GPPGA for a given patient is not performed by the same physician throughout the study.	None #
F2.03	Temperature recordings for a given patient not made at the same area throughout the study	Not all recordings for a given patient made in ear or oral cavity, respectively.	None
G	Other safety related violations		
G1	Pregnancy test not done for woman of child bearing potential at Visit 12, 12pc, 13, 13pc, or 14		None #

# PV will be detected manually.

Violations F2.01 and F2.02 can only be detected at the trial site.

Source: BI reference document 'Protocol Violation Handling Definitions' [001-MCS-50-413\_RD-01] ([2](#)).

## **6.3 PATIENT SETS ANALYZED**

The following analysis sets will be defined for this trial:

- **Enrolled set (ES):**  
This patient set includes all patients who signed informed consent.  
It will be used for analyses of patient disposition.
- **Entered set (ENT-S):**  
This patient set includes all entered patients (as identified by the investigator in the eCRF), whether treated or not.  
It will also be used for analyses of patient disposition.
- **Treated set (TS):**  
This patient set includes all patients in the ENT-S who received study drug at Visit 3.  
It will be used for analysis of safety data.
- **Full analysis set (FAS):**  
This patient set includes all patients in the TS who had a baseline and at least one post-baseline measurement available for GPPASI or GPPGA without any IPV flagged for exclusion from the FAS in the table above.  
This is the main analysis set for presentation of efficacy.
- **Per protocol set (PPS):**  
This patient set includes all patients in the FAS who adhered to the CTP without any IPVs which are flagged for exclusion from the PPS in the table above.  
The PPS will be used for sensitivity analysis of secondary efficacy endpoints.
- **Pharmacokinetic parameter set (PKS):**  
This patient set includes all patients in the TS who provide at least one observation for at least one secondary PK endpoint, which was not flagged for exclusion. PK parameters (and blood and plasma concentrations) can be flagged for exclusion due to a protocol violation relevant to the evaluation of PK (to be decided no later than in the RPM) or due to PK non-evaluability (as revealed during data analysis, based on the criteria specified below). Exclusion of a patient's data will be documented in the CTR.  
Relevant IPVs are documented in [Table 6.2: 1](#) above.  
Plasma and blood concentrations and/or parameters will be considered as non-evaluable, if e.g. a pre-dose concentration is >5% of the  $C_{max}$  value of that patient, or if relevant time deviations occurred (as identified no later than in the RPM), or due to use of restricted medications (as identified no later than in the RPM).  
**CTP:** *It will be decided in the Report Planning Meeting which patients are to be included in the PKS.*  
This patient set will be used for the descriptive analysis of concentrations and PK parameters.

The discussion of all exceptional cases and problems and the decisions on the allocation of patients to populations will be made at latest at the RPM/DBLM.

Table 6.3: 1 illustrates the data sets which are to be used for each category class of endpoints, and the approaches used with regard to missing data. For explanation of the different methods of handling missing data, cf. [Section 6.6](#).

Table 6.3: 1 Patient sets analyzed

Class of endpoint	Patient set					
	ES	ENT-S	TS	FAS	PPS	PKS
Disposition	OR	OR	OR			
Compliance and exposure			OR	OR		
IPVs		OR				
Demographic/ baseline characteristics				OR		
Primary endpoint			OR			
Secondary efficacy endpoints				LOCF  , NRI  , OC-IR  , OC 	LOCF  , NRI  ,OC 	
Secondary PK endpoints					OR	

 secondary analysis

 sensitivity analysis

 only for percent reduction from baseline in GPPASI total score, change from baseline in FACIT-Fatigue scale score and change from baseline in Pain VAS

 only for proportion of patients with GPPGA total score of 0 or 1

For explanation of the different approaches with regard to missing data see [Section 6.6](#).

"LOCF" and "NRI" means analyses involving imputed data, cf. [Section 6.6.2](#).

OC = observed cases, OC-IR = observed cases including also values after rescue medication, OR = original results.

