7.3.2 Secondary analyses

The continuous secondary efficacy endpoints, such as GPPASI total score, Pain VAS, and FACIT-Fatigue score at week 2, will be evaluated descriptively, including the original as well as change from baseline values where applicable, along with exact 95% confidence intervals, if feasible. For the GPPASI total score, the percentage change from baseline at week 2 will be displayed.

The binary efficacy endpoint, GPPGA response of 0 (clear) or 1 (almost clear), will be described using patient frequencies and percentages. Exact 95% confidence intervals will additionally be provided for the proportion of patients with a response, if feasible.

The patient set for the evaluation of efficacy endpoints (FAS) will include all treated patients who had a baseline and at least one post-baseline measurement available for either GPPASI or GPPGA. Baseline is defined as the last measurement collected prior to administration of the trial treatment.

Proprietary confidential information © 2016 Boehringer Ingelheim International GmbH or one or more of its affiliated companies

The secondary PK parameters (refer to [Section 5.5.1](#)) will be calculated according to the BI Standard Operating Procedure (SOP) 'Standards and processes for analyses performed within Clinical Pharmacokinetics/Pharmacodynamics' ([001-MCS-36-472](#)). Analyses will be performed for parent drug.

Pharmacokinetic parameters of a patient will be included in the analysis unless the patient has an important protocol violation relevant for the evaluation. Whether a protocol violation is important will be decided no later than in the Report Planning Meeting.

Reasons for exclusion of single pharmacokinetic parameters may be:

- Time deviations
- Use of restricted medications

The patient set for the evaluation of PK endpoints (PKS) will include all treated patients that provide at least one observation for at least one secondary PK endpoint without important protocol violations with respect to the statistical evaluation of PK endpoints. It will be decided in the Report Planning Meeting which patients are to be included in the PKS.

Excluded patients will be listed with their individual plasma concentrations and individual pharmacokinetic parameters, however, will not be included in descriptive statistics for plasma concentrations, pharmacokinetic parameters or other statistical PK assessment.

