#### **4. CHANGES IN THE PLANNED ANALYSIS OF THE STUDY**

The following analyses described in this TSAP are new/adapted analyses from those specified in the revised CTP.

- For secondary efficacy endpoints of a continuous nature, it was specified in the CTP that exact 95% confidence intervals around the mean will be produced. Per specification in [Section 7.5.2.1](#), the 95% confidence intervals for continuous data will be based on the t-distribution.

In the CTP it is stated that analyses of immunohistochemistry and flow cytometry will be conducted. These analyses will not be carried out for the CTR, but may be done at a later time point (depending on the obtained results). In case they are performed at a later time point, the analysis details will be described in a separate document.

In the CTP, it was noted that a logistics plan will be developed to protect the integrity of the trial data once the week 4 analyses has been performed. However, since at this time the final analysis of the efficacy and safety data up to week 4 will be complete, and because no further patient dosing visits are planned, the week 4 results may be made available and published to support enrolment into subsequent trials in this and potentially other indications of BI 655130.

The following analyses described in this TSAP are new/adapted analyses from those specified in the signed version of the TSAP, dated 4 OCT 2017:

- Section 6.2  
Definition of IPV: exclusion criteria 8 (i.e. use of restricted medication prior to the study) was modified from a programmatic to a manual assessment. This was done in order to ensure that medical decision could be made on whether such occurrence of an IPV would or would not affect the assessment on efficacy.

Same consideration was also applied to IPV D2.01 (and D2.02) representing prohibited medication use during the study.

- Section 6.6.2  
LOCF imputation was clarified to confirm that the baseline value would be carried forward in the event of no available post-baseline data (and not just in the case when missing post-baseline data was driven by rescue medication taken immediately after the first dose).
- Section 6.6.9  
Additional imputation strategies, for summary reporting only, are presented for the handling of cases where incomplete data are reported for previous GPP flare occurrences.

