### Binary efficacy endpoints

Some efficacy endpoints are defined in terms of the proportion of patients with a particular binary outcome, i.e. achievement of a GPPGA total score of 0 or 1. For those binary outcomes, the different methods for handling of missing data, presented below, will be performed as presented in Table 6.3: 1. Please note that some of these binary outcomes are derived from other parameters, but imputation is planned to take place only at the binary level, i.e., the GPPGA total score itself will not be imputed, but the binary endpoints derived based on these scores will be imputed.

- The following primary imputation strategy ("NRI") will be performed:
  - If there are data at the visits both immediately before and immediately after the visit with a missing outcome, then impute as success only if both the preceding and the following observations also represent a success (independent of whether the preceding and following observations were selected for analysis based on time windows described in [Section 6.7](#));
  - Otherwise, impute as a failure to achieve a response (i.e. no response imputation [NRI]).

For patients who take a rescue medication (as defined in [Section 5.3.4](#)) during the course of the study, all efficacy outcomes measured after the day of first use of rescue medication will be set to missing and, during the on-treatment period, will be imputed using the steps described above.

- Observed cases (OC) approach will be used as a sensitivity analysis and will include all collected data, with no imputation performed on the missing data. Such an OC approach will exclude all values measured after intake of a rescue medication (i.e. such values will be set to missing).
- Observed cases including rescue (OC-IR) approach will be used as a further sensitivity analysis and is an extension of the OC approach which includes additionally all values which were measured after rescue medication intake.

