## **7.2 CONCOMITANT DISEASES AND MEDICATION**

Analyses of concomitant diseases and medication will be based on the FAS.

Concomitant diseases will be coded according to the most recent version of MedDRA. Concomitant medication will be coded according to the most recent version of the World Health Organisation – Drug Dictionary.

Signs/symptoms of the trial disease (as identified on the eCRF) will be summarized separately from other concomitant diseases, by system organ class and preferred term.

Other characteristics of the trial disease, such as the frequency and percentage of resolved flares within the last 12 months, as well as details on the shortest, longest, and last GPP flare which occurred prior to admission into this trial, will be displayed. The duration (up to start of treatment) and likely cause of the current flare of GPP will also be presented. The "number of flares of GPP that resolved with treatment" will be calculated as the number of resolved flares of GPP in previous 12 months minus the number which resolved spontaneously without treatment.

A medication will be considered concomitant to treatment, if it

- is ongoing at the start of trial treatment or
- starts within the analysis phase of the trial treatment (see [Section 6.1](#) for a definition of treatments and analysis phases).

Concomitant medication use (excluding rescue medication on or after Visit 2 and before end of the on-treatment period, historical medication for GPP and background medication) will be summarized with frequency and percentage of patients by ATC3 class and preferred name. Summaries will be presented for

- concomitant therapies taken any time prior to Day 1 (the day of start of trial treatment),
- concomitant therapies initiated on Day 1, and
- concomitant therapies taken any time during the on-treatment period (cf. Section 6.1).

The frequency and percentage of patients with previous treatment on methotrexate, retinoids, cyclosporin, and other historical medication for GPP will be displayed, and will include an assessment of those patients who continue to take methotrexate or retinoids as background medication in this trial. Here, background medication is defined as any administration of methotrexate or retinoids which is ongoing on the day of administration of BI 655130. In addition, the time since last dose relative to Visit 2 for patients who have discontinued prior methotrexate or retinoid use will be listed.

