### **7.5.2 Secondary endpoints**

#### **7.5.2.1 Secondary efficacy endpoints**

Analysis of secondary efficacy endpoints will be based on the FAS; an analysis based on the PPS will be performed as a sensitivity analysis. The analysis of imputed values (cf. [Section 6.6.2](#)) will be considered the main approach for secondary efficacy analyses of this trial. Other analysis approaches based on the FAS (and on the PPS) will be considered sensitivity analyses to assess the impact of missing data, intake of rescue medication, and IPVs on the efficacy outcomes.

The GPPASI total score and the percent reduction from baseline in GPPASI total score will be summarized descriptively by visit as will the FACIT-Fatigue scale total score and pain VAS score; the changes from baseline at each post-baseline visit will also be displayed. For the percent reduction from baseline in GPPASI total score as well as the change from baseline in FACIT-Fatigue scale total score and pain VAS at each visit, 95% confidence intervals around the mean will be presented and are calculated as follows:

$$\left( \text{mean} - t_{n-1; 0.975} \frac{SD}{\sqrt{n}}; \text{mean} + t_{n-1; 0.975} \frac{SD}{\sqrt{n}} \right),$$

where "mean" denotes the sample mean, "SD" denotes the sample standard deviation, "n" denotes the number of non-missing values in the sample, and " $t_{n-1; 0.975}$ " denotes the 0.975 quantile of the t-distribution with  $n-1$  degrees of freedom.

Graphical presentations of the mean and 95% confidence interval by visit will be provided for percent reduction from baseline in GPPASI total score, change from baseline in FACIT-Fatigue scale total score and change from baseline in pain VAS score. Additionally, for percent reduction from baseline in GPPASI total score, 95% confidence intervals for the median will be calculated based on the SAS procedure PROC UNIVARIATE with option CIPCTLDF, and graphical presentations of the median and 95% confidence interval by visit will be provided.

For the FACIT-Fatigue scale, frequencies of patients with each score for each of the individual questions will additionally be summarized by visit.

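### A treated patient who is never scored after dosing leaves the FAS and is not counted as a Week 2 failure in any planned analysis

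*SAP*

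**What the plan says.** Protocol 7.3.2 defines the efficacy set as "all treated patients who had a baseline and at least one post-baseline measurement available for either GPPASI or GPPGA". SAP 6.3 keeps that condition: "This patient set includes all patients in the TS who had a baseline and at least one post-baseline measurement available for GPPASI or GPPGA". It adds that the patient must have no important protocol violation (IPV) flagged for FAS exclusion.

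SAP 7.5.2.1 then fixes where the set is used: "Analysis of secondary efficacy endpoints will be based on the FAS; an analysis based on the PPS will be performed as a sensitivity analysis". SAP 6.3 builds the PPS from FAS members only. Table 6.3: 1 lists secondary efficacy under the FAS and PPS, with nothing under the TS. SAP section 7 takes percentages over all patients in the set concerned, whether or not they have a value.

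For missing outcomes the SAP is conservative. Under the binary rule, a missing response that is not flanked by two successes falls to the default: "Otherwise, impute as a failure to achieve a response". For continuous endpoints, the last available value, including baseline, is carried forward, and SAP section 4 adds: "LOCF imputation was clarified to confirm that the baseline value would be carried forward in the event of no available post-baseline data".

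The descriptive tables follow the FAS as well. SAP 7.1 does so for demographics and baseline characteristics, and SAP 7.2 states: "Analyses of concomitant diseases and medication will be based on the FAS". The primary endpoint, patients with drug-related adverse events, is analysed on the TS.

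**The concern.** Membership of the main efficacy set depends on something that happens after dosing. The two imputation rules already say how a patient without follow-up scores should be handled: as a non-responder for GPPGA 0/1, and with no change from baseline for GPPASI. They act only on patients already admitted to the set. A patient with neither score after dosing is not admitted, so the rules never reach the case with the least information.

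The trial plans 6 to 10 patients, is meant to establish proof of clinical concept (protocol 2.2) and is to inform health authority discussions (protocol 2.1). At that size one patient visibly changes a response rate. A patient removed this way would also count in the primary-endpoint denominator while being absent from the demographic and medication tables that describe the treated group.

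**Working it through.** **Plan's own figure.** There is none to reproduce. Protocol 7.6 bases the sample size on feasibility and gives no expected response rate. The response counts below are assumptions.

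**Step 1: can any planned analysis restore the patient?**
- Main analysis: FAS with NRI or LOCF. The patient is not in the FAS.
- Observed-cases analyses, with and without values after rescue: run within the FAS (and observed cases also within the PPS). Not included.
- PPS analyses: the PPS is drawn from the FAS. Not included.
- TS: no secondary efficacy analysis is listed.

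So the answer is no.

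**Step 2: size for the response rate.** Let N be treated patients, r responders, and let one treated patient be never scored after dosing.
- Plan: r/(N−1)
- All treated, with that patient as a non-responder: r/N
- Difference: r/(N−1) − r/N = r/[N(N−1)], which is never negative.

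SAP 7.5.2.1 names Wilson score intervals. With p = r/n and z = 1.96, the lower limit is [p + z²/(2n) − z√(p(1−p)/n + z²/(4n²))] / (1 + z²/n). For 4/5: (0.8 + 0.3842 − 1.96 × √(0.0320 + 0.0384)) / 1.7683 = (1.1842 − 0.5201) / 1.7683 = 37.6%.

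| N | r | All treated, r/N (Wilson lower) | Plan, r/(N−1) (Wilson lower) | Difference, points |
|---|---|---|---|---|
| 6 | 4 | 66.7% (30.0%) | 80.0% (37.6%) | 4/30 = 13.3 |
| 8 | 6 | 75.0% (40.9%) | 85.7% (48.7%) | 6/56 = 10.7 |
| 10 | 7 | 70.0% (39.7%) | 77.8% (45.3%) | 7/90 = 7.8 |

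Over a wider set of assumed counts, one such patient moves the rate by between 5.6 points (N = 10, r = 5: 5/90) and 16.7 points (N = 6, r = 5: 5/30). If no treated patient goes unscored, the shift is zero.

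**Step 3: continuous endpoints.** Carrying baseline forward gives the patient a change of 0. If the other N−1 patients have mean GPPASI reduction m, the all-treated mean is m(N−1)/N. For positive m, leaving the patient out keeps the mean at m when it would otherwise be lower by one sixth (N = 6) to one tenth (N = 10) of m.

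**Step 4: IPV D1.02 against SAP section 4.** D1.02 is titled as rescue use before study drug. Its comment column applies it to any rescue on the day of Visit 2 or Visit 3, because clock time is not reported, and it excludes from the FAS and PPS. Visit 3 is the infusion day, so a patient rescued after the infusion that day is also removed. SAP section 4, however, refers to post-baseline data missing because of rescue taken immediately after the first dose, with baseline carried forward, which presupposes that the patient is analysed. Under SAP 6.6.2, values after the day of first rescue are set to missing, so rescue on Day 1 is the natural case in which a GPPASI baseline would be carried forward for that reason, and D1.02 takes that patient out of the set. The SAP also does not say whether scores set to missing after rescue still count as available for FAS entry.

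**The case against.** The strongest reply is that the route is very narrow. FAS entry needs one post-baseline value of either score, with no time limit. Scores are taken daily from Day 2 to Day 7, and patients stay in hospital for at least 4 days after dosing. Rescued patients remain in follow-up to Day 140 (protocol 4.2.1.1). A complete V12 examination, which includes both scores, is required at discontinuation (protocol 3.3.4.1). Immediately life-threatening flares are excluded at entry. All of this stands. A reader might infer that any patient who fails or is rescued early leaves the FAS, but the documents do not support that. A patient rescued on Day 2 or later who is scored stays in, and the binary rule normally counts that patient as a failure.

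A reader might also infer that the FAS definition can only favour the drug. That holds for a patient never scored after dosing. It does not hold for one lost only for lack of a baseline, for example because the Day 1 scores were timed after the infusion began (Table 6.7: 1, footnote A). That is a scheduling error, and the patient may be a responder: 4/6 (66.7%) would become 3/5 (60.0%). That exclusion loses data without a fixed direction.

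Nor is the baseline-carried-forward rule made empty. FACIT-Fatigue and pain VAS are first repeated at Visit 9, so a FAS member lost before then has those baselines carried forward.

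Finally, an excluded patient is not hidden. Exposure is tabulated on the TS, individual values are listed and analysis-set counts are reported, so a reader could recompute the rate. This limits the harm, but it leaves the headline proportion computed on a selected denominator.

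**Conclusion.** The point holds in limited form. A treated patient with no GPPASI or GPPGA value after dosing is outside every planned efficacy analysis, and neither the non-response rule nor the baseline-carried-forward rule can reach that patient. For such a patient the effect favours the drug, by about 6 to 17 percentage points of response in the cases computed, given one exclusion among 6 to 10 treated patients and the assumed response counts. The likely number of such patients is small or zero.

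The primary endpoint is unaffected because it uses the TS. Efficacy is secondary and descriptive, with no hypothesis test, so no error rate or power is at stake. This is an inexpensive improvement to the definition of the main efficacy set. D1.02 and SAP section 4 do need reconciling, because as written they treat rescue on the infusion day differently.

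**What to change.** - Remove the post-baseline condition from the FAS, so that it is the TS less patients with an FAS-excluding IPV. At minimum, add a TS analysis of GPPGA 0/1.
- In that analysis, score never-scored patients as non-responders and carry baseline forward for continuous endpoints, as SAP 6.6.2 already provides. The current FAS can be kept as a sensitivity set.
- Do not require a baseline for GPPGA 0/1 at Week 2, which is not a change score. This only avoids losing data.
- Record the departure from protocol 7.3.2 in SAP section 4, since the protocol itself defines the set.
- Tabulate demographics and concomitant medication on the TS, the set used for the primary endpoint.
- Reconcile IPV D1.02 with SAP section 4 on rescue taken on the day of Visit 3, and state whether scores set to missing after rescue count as available for FAS entry. Removing the post-baseline condition alone does not settle this, because D1.02 would still exclude the patient.

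The cost is SAP wording and, at most, one extra table. No new data are collected. The downside is that the reported response rate may be less favourable.
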